4.2.2 Variables Assessed by Questionnaires Administered at the Study Site

NOTE: Standard definitions for flatulence and fecal incontinence will be included in the study procedure manual

Excessive Flatulence

Excessive flatulence (NOTE: the term “excessive” is meant to be interpreted by each patient in terms of what he/she perceives as “more than normal” either for him or herself or as compared to his peers/friends) will be assessed via the IWRS at each study visit. Patients will be asked to rate their “excessive flatulence” using the IWRS on a scale from 0 to 4, where 0 = none, 1 = mild, 2 = moderate, 3 = severe, and 4 = very severe.

Fecal Incontinence

The following question will be asked at each study visit using the IWRS as follows:

Visit 1:

Have you ever experienced fecal incontinence? YES NO

If YES, Approximately how many episodes of fecal incontinence did you experience over the last two weeks?

0 1 2 3 more than 3

Visits 2 through 5:

Approximately how many episodes of fecal incontinence did you experience over the last two weeks?

0 1 2 3 more than 3

Three standardized patient questionnaires (see **Appendix E**) will also be administered during the scheduled study site visits to assess the severity of constipation and impact of the disease on the patient’s quality of life.

Patient Assessment of Constipation—Symptoms (PAC-SYM)

The PAC-SYM is a previously validated questionnaire which is made up of 12 questions addressing specific symptoms of constipation. The patient will be asked to rate each symptom on a scale of 0 (“absent”) to 4 (“very severe”).

Patient Assessment of Constipation—Quality of Life (PAC-QOL)

The PAC-QOL is a previously validated questionnaire is made up of 28 questions which assess how the patient has been impacted by constipation over the specified period. The questions measure worries and concerns, physical discomfort, psychosocial discomfort, satisfaction, and overall effects on the patient’s quality of life. Patients will be asked to give their response on a scale of 0 (“not at all” or “none of the time”) to 4 (“extremely” or “all of the time”).

Patient Global Assessment (PGA) Questionnaire

The Patient Global Assessment (PGA) questionnaire is designed to provide an assessment of constipation severity before, during, and after treatment. The PGA is reproduced in **Appendix E**.

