Study Design	
This is a randomized, double-blind, placebo-controlled, multicenter, parallel-group study of the efficacy and safety of 3 dose levels of plecanatide (0.5, 1.0, or 1.5 mg) in adolescent patients 12 to less than 18 years of age with CIC. Patient randomization will focus on the balanced enrollment of males and females across the 4 treatment groups.
 
This Phase 2b study will comprise a 28-day bowel habit Screening/Baseline Period, an 8-week Treatment Period, and a 2-week Posttreatment Follow-up Period. Patients will visit the clinic 5 times during the study.
 
Screening/Baseline Period: Patients' legally authorized representatives (e.g., parent or guardian) will provide informed parental permission and patients will provide written assent before they undergo any protocol-specified procedures or assessments. At the Screening visit, patients will undergo a review of medical history, a review of prior and concomitant medications, a brief dietary history, and physical examination. During the 28-day Screening/Baseline Period prior to randomization, patients will record - through an electronic diary - daily assessments of bowel movements (BMs), stool consistency (using the Bristol Stool Form Scale [BSFS]), abdominal pain, abdominal discomfort, abdominal bloating, straining and pain when passing stools, fecal incontinence, excessive flatulence, and feeling of incomplete evacuation following bowel movement. Data from the electronic diary will be used to confirm study eligibility immediately prior to the randomization visit, as well as to characterize the patient's baseline chronic constipation status with which the change from Baseline across and at the end of the 8-week treatment period will be compared.
 
Treatment Period: Patients who meet all entry criteria will be randomly assigned to 1 of 4 treatment groups (3 active, 1 placebo) in a 1:1:1:1 ratio on Day 1 of the Treatment Period. Randomization will be stratified to ensure gender balance across treatment groups. Patients will take an oral dose of the study drug once daily for 8 weeks and continue to complete their daily electronic diaries with recording of

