2.4.1.3 Additional Efficacy Endpoints

Additional efficacy endpoints related to CIC symptoms are:

- Change from baseline in abdominal pain, by study week
- Change from baseline in abdominal bloating, by study week
- Change from baseline in straining during a BM, by study week
- Change from baseline in pain with defecation, by study week
- Change from baseline in excessive flatulence, by study period
- Change from baseline in frequency of fecal incontinence, by study period

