6.2 ADMINISTRATION

Study drug will be administered for 8 consecutive weeks according to the randomization scheme displayed in **Table 3**. Each patient will take one tablet orally (by mouth) daily preferably at the same time each day—**in the morning**—with approximately 240 mL (~8 oz.) of liquid, with or without food.

No dose adjustments will be allowed on this study.

Table 3 Treatment Arms

Table 3: Treatment Arms

Treatment Arm	Treatment	Number of Patients
1	0.5 mg plecanatide	30
2	1.0 mg plecanatide	30
3	1.5 mg plecanatide	30
4	Matching placebo	30

Overdose

Plecanatide has minimal systemic absorption, therefore standard treatment measures for the symptomatology being exhibited should be provided. Notable, plecanatide was generally well-tolerated after single doses up to 48.6 mg and multiple doses up to 9.0 mg for 12 weeks in prior studies.

Individual Patient Stopping Criteria

Adverse events due to study drug that affect individual patient safety may necessitate dose interruptions or early discontinuation as described in this section.

Plecanatide therapy in adults with CIC has caused diarrhea in 5% of patients with severe diarrhea occurring in 0.6% of patients. Severe diarrhea may cause dehydration. Pediatric patients may be at increased risk for diarrhea and dehydration with plecanatide therapy.

In general, study drug dosing should not be modified for mild diarrhea (Grade 1: increase of <4 stools per day over baseline) or mild dehydration (Grade 1: dry mucous membranes, diminished skin turgor) (Guidance for Industry, FDA, 2007). If study drug is not well tolerated by an individual patient, treatment will be permanently discontinued for that patient.

The following guidelines should be used in the case of moderate or severe diarrhea or dehydration:

Table 4 Individual Patient Stopping Criteria

Worst Observed Toxicity Grade (Guidance for Industry, FDA, 2007)	Dose Modification for Study Drug
Diarrhea	
Grade 2: Increase of 4-6 stools per day over baseline	No intervention required
Grade 3: Increase of ≥ 7 stools per day over baseline, incontinence, hospitalization indicated	Interrupt study drug for <7 days until resolved to less than Grade 2 severity. If diarrhea was study drug-related, permanently discontinue study drug. If diarrhea was not study drug-related, eg, viral gastroenteritis, then consider resuming treatment after consultation with Sponsor's Medical Monitor

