9.9 DURATION OF THE STUDY

For an individual patient, the planned duration of the study will be 98 days (including 28 days for screening, 56 days of treatment and 14 days of follow-up).

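### Fecal incontinence is a daily diary item in the Synopsis but is asked only at visits in the body of the protocol, leaving about half of the treatment period without a systematic count and the top answer open-ended

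*Combined protocol and SAP*

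**What the plan says.** The Synopsis (Study Design, Screening/Baseline Period) describes daily electronic diary assessments that include "straining and pain when passing stools, fecal incontinence, excessive flatulence, and feeling of incomplete evacuation following bowel movement".

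The body of the protocol does something else. Section 4.2.1 names five diary symptoms: abdominal pain, bloating and discomfort, straining, and pain with defecation. The diary script in Appendix D has the same five. Fecal incontinence appears instead in Section 4.2.2, among the site questionnaires: "The following question will be asked at each study visit using the IWRS as follows". From Visit 2 on, the wording is "Approximately how many episodes of fecal incontinence did you experience over the last two weeks", with the answers "0 1 2 3 more than 3". Section 8.8.5 treats the result as questionnaire data.

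Section 2.4.1.3 makes it an additional efficacy endpoint: "Change from baseline in frequency of fecal incontinence, by study period". Section 8.8.3 does not repeat it. Table 4 in Section 6.2 also names incontinence in its Grade 3 diarrhea row: "Increase of ≥ 7 stools per day over baseline, incontinence, hospitalization indicated".

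**The concern.** Two things are at issue. First, the documents disagree on how the item is collected. A data manager building the diary from the Synopsis and one building it from Appendix D would collect different data.

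Second, the visit question is a thin measure of a frequency. It looks back two weeks from visits that are about four weeks apart during treatment, so it skips the first part of each interval, including the start of dosing. Its top category is open, so it stops distinguishing patients once they have four or more episodes in two weeks. An endpoint described as change in frequency by study period would then rest on about half of the Treatment Period, with change at the upper end invisible in both directions. Nothing else fills the gap systematically: PAC-SYM and PAC-QOL have no incontinence item, and the bowel movement diary records number, time, completeness and form, but not continence.

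**Working it through.** **Inputs**

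- Recall: 14 days (Section 4.2.2, Visits 2 to 5).
- Visits: "Patients will visit the clinic 5 times during the study" (Synopsis). These are Day -28, Day 1, Day 28 (±3), Day 56 (+3) and Day 70 (+3) (Table 2; Sections 5.2.1 to 5.2.5). The Week 1 visit in the Synopsis is Day 1, so no clinic visit falls between Day 1 and Week 4.
- Length: "including 28 days for screening, 56 days of treatment and 14 days of follow-up" (Section 9.9). Check: 28 + 56 + 14 = 98 days, as stated there.

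**Coverage**

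A visit on Day v covers Days v−13 to v if the visit day counts, or v−14 to v−1 if it does not. At Visit 2 the questionnaires are completed before dosing (Section 5.2.2), so that answer is entirely pre-dose.

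At nominal dates, with the visit day counted:

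- Visit 3 (Day 28) covers Days 15-28.
- Visit 4 (Day 56) covers Days 43-56.
- Visit 5 (Day 70) covers Days 57-70, after treatment.
- Covered: 14 + 14 = 28 of 56 days. Not covered: Days 1-14 and 29-42, which is 28 of 56 (50%).

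Across the visit windows, with Visit 5 on Day 70 (visit day counted / not counted):

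| Visit 3 | Visit 4 | Days covered | Days not covered | Uncovered days at the start |
|---|---|---|---|---|
| 25 | 56 | 28 / 29 | 28 / 27 | 11 / 10 |
| 28 | 56 | 28 / 29 | 28 / 27 | 14 / 13 |
| 31 | 56 | 28 / 29 | 28 / 27 | 17 / 16 |
| 25 | 59 | 25 / 26 | 31 / 30 | 11 / 10 |
| 28 | 59 | 25 / 26 | 31 / 30 | 14 / 13 |
| 31 | 59 | 25 / 26 | 31 / 30 | 17 / 16 |

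Moving Visit 5 to Day 73 stays within these limits. The uncovered part is 27 to 31 of 56 days (27/56 = 48%; 31/56 = 55%), and the uncovered initial run is 10 to 17 days.

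**Top category**

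More than 3 episodes in two weeks means 4 or more, or an average above 3/2 = 1.5 per week. Falling from 10 to 5, or rising from 4 to 12, leaves the answer unchanged.

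The documents do not say how many patients start there. As an illustration only, assume Poisson counts with weekly rate λ, so the two-week mean is 2λ and the share in the top category is P(X > 3):

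| Assumed rate per week | Two-week mean | Share in top category |
|---|---|---|
| 0.5 | 1 | 2% |
| 1 | 2 | 14% |
| 2 | 4 | 57% |
| 3 | 6 | 85% |
| 5 | 10 | 99% |

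One of the Rome III criteria in Appendix A is at least one episode per week, about 2 per recall. Patients meeting it can start near or in the top category, but need not, and the criterion is not required for entry.

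**The case against.** The best defense is that this is sampling at landmarks, done consistently. Visit 2 looks back over the 14 days before dosing, the same window as the baseline diary (Section 8.4.3). Later visits use the same recall, so change from baseline compares equal windows. PAC-SYM and PAC-QOL also use two weeks. The endpoint is specified by study period, whereas the diary symptoms are by study week. All of this stands: the visit question is coherent, and the contradiction could be closed by correcting the Synopsis alone. What it does not supply is a count for the other half of treatment, or for anyone above 3.

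Four stronger readings are tempting, and the documents do not support them.

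- *Early episodes go unobserved unless the patient volunteers them.* Section 4.3.1 requires open questioning that reaches back to the previous visit, and incontinence is not among the symptoms kept out of adverse event recording. An Early Withdrawal visit, due within 5 days of stopping drug, repeats the questionnaires (Section 5.2.6). These routes exist, but they do not give a systematic count.
- *Drug-related incontinence would appear first in the uncovered early days.* The 12.5-hour figure in Section 2.1.4 is median time to first SBM in adults at 3.0 mg, twice the highest dose here. The documents give no incontinence data for plecanatide.
- *The Synopsis promises a daily item throughout the study.* Its list belongs to the Screening/Baseline Period. For treatment it names BMs, rescue use, abdominal pain and unspecified other symptoms.
- *Grade 3 diarrhea would be missed.* Stool frequency and form are recorded for each BM, and adverse events are collected. The point is only that no scheduled question records incontinence as it happens.

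The final diary text and the questionnaire timing are deferred to documents not available here (Appendix D; Table 2, footnote j). Section 4.2.2 nonetheless ties this question to visits.

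**Conclusion.** The point holds as an inconsistency and an inexpensive gap in measurement. The Synopsis and Sections 4.2.1, 4.2.2, 8.8.5 and Appendix D must be reconciled. As the body stands, 28 of 56 treatment days at nominal dates have no systematic count of fecal incontinence. The open top category hides worsening in a patient who starts there, and any improvement that stays above 3.

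The coverage figures rest only on the stated recall and visit days, counted to Day 56. How much the cap matters rests on baseline rates that the documents do not give.

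The consequence is limited to one additional endpoint and to how well tolerability can be described. The primary and key secondary analyses are not affected.

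**What to change.** Add one item to the End-of-Day diary, asking for the number of fecal incontinence episodes that day, from the start of the two-week baseline diary through Week 10. Amend Sections 4.2.1, 4.2.2, 8.8.5 and Appendix D to match, and derive the endpoint as a weekly rate.

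Base that rate on the days actually recorded. The convention in Section 8.4.1 that counts missing days as zero is conservative for SBMs, but would be favorable for incontinence.

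In principle this raises coverage from 28 to 56 of 56 treatment days and removes the cap. The cost is one more question in a call that patients already make daily, and a change to a script that Appendix D says is not yet final.

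If the visit question is kept, leave the two-week recall the same at every visit and record the actual count in place of the open category. Do not extend the recall to run from the previous visit. At nominal dates that would span about 27, 28 and 14 days at Visits 3, 4 and 5 against 14 at baseline, so at a constant rate the raw count would rise by a factor of 27/14 = 1.9 at Visit 3 and 28/14 = 2.0 at Visit 4 with no real change.

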4.3 SAFETY VARIABLES

4.3.1 Collection of Adverse Events

It is the responsibility of the Investigator to ensure that all AEs are collected. This includes both serious and non-serious AEs derived by spontaneous, unsolicited reports of patients, by observation, and by routine open questionings e.g., “How have you felt since I last saw you?”

NOTE: Specific GI symptoms are recorded daily in the GI symptom diary (abdominal bloating, abdominal pain, abdominal discomfort, straining with a bowel movement and pain with defecation) in response to standardized questions. The frequency and severity ratings recorded for these symptoms are both an efficacy and safety record and therefore these events should generally NOT be recorded elsewhere as adverse events.

For Definitions, Assessments of AEs, Causality, Severity, Recording and Reporting of Adverse Events and Follow Up, see **Section 7**.

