2.4.3 Safety Endpoints

The following safety endpoints will be assessed:

- Frequency of treatment-emergent adverse events (TEAEs)
- Withdrawals due to adverse events and serious adverse events

Clinically important changes in laboratory tests, vital signs, and ECGs will be presented.

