7 ASSESSMENT, REPORTING, RECORDING AND FOLLOW UP OF ADVERSE EVENTS

7.1 DEFINITION

An AE is any untoward medical occurrence associated with the use of a drug in humans, whether or not considered to be drug related. An AE can therefore be any unfavorable and unintended sign (including abnormal laboratory finding), symptom, or disease temporally associated with the use of an investigational product or study procedure whether or not considered related to the product or procedure.

NOTE: Specific gastrointestinal symptoms related to CIC are recorded daily in the electronic Diary in response to standardized questions, and are BOTH efficacy AND safety response variables. These symptoms are abdominal bloating, abdominal pain, abdominal discomfort, straining with bowel movement and pain with defecation. The diary is a “real-time” patient reported outcome record that is based on “within 24 hours” patient recall. Because these symptoms are considered adequately recorded in the CIC Symptom Diary, they should generally not also be reported in the adverse event database that relies on a much longer patient recall period. In order to prevent double-recording of a single specific event, the daily CIC Symptom Diary record is considered the highest quality record of an event and should therefore be the only record of the same event.

All AEs, including intercurrent illnesses and regardless of the source of identification (e.g., physical examination, laboratory assessment, electrocardiogram (ECG), reported by patient), occurring during the study will be documented in the eCRF. Concomitant illnesses that existed before entry into the study will not be considered AEs unless they worsen during the treatment period.

Adverse events occurring from the time of signing the informed consent form (ICF) up to the intake of the first dose of study medication will be classified as pre-existing conditions for the study and therefore will be recorded in the Medical History page of the electronic case report form (eCRF). Serious adverse events (as defined below) occurring after the signing of informed consent but before randomization (i.e., during screening) will be collected and reported as such. A treatment emergent adverse event (TEAE) is defined as an AE that begins or worsens in frequency and/or severity after at least one dose of study drug has been administered.

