8.8.3.1 Analysis of the Additional Efficacy Endpoints

The weekly average of each additional efficacy endpoint score (abdominal pain, abdominal bloating, abdominal discomfort, straining during a bowel movement, or pain with defecation) for each patient will be computed, as described in Section 8.4.1, for each week of the 8-week treatment period and for the two weeks of the follow-up period. A summary, by treatment group, of the mean weekly average symptom score, and change from baseline in mean weekly average symptom score, for each of the 10 study weeks will be presented. The change from baseline in mean weekly average symptom score will be analyzed using a linear mixed-effects model with fixed effects for gender (stratification variable), treatment, week, the interaction of treatment and week, and the corresponding baseline value; a random intercept for patient will also be specified. For each abdominal symptom score, the least squares (LS) mean change from

baseline will be presented, and the difference in LS means for each plecanatide treatment group compared to placebo will be presented, with 95% confidence interval and corresponding statistical *p*-value, for each week of the 8-week treatment period and for the two follow-up weeks.

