8.8.5 Patient Reported Outcomes

PRO questionnaire data for fecal incontinence, excessive flatulence, PGA, PAC—SYM, and PAC—QOL will be included in the patient listings. Summary analyses of these data will also be provided as described in the SAP.

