8.10 SAFETY ANALYSES

Evaluation of the safety of once daily plecanatide over 8 weeks of dosing will be based on the occurrence of TEAEs, vital signs, clinical laboratory assessments, and ECGs and as compared with those noted in the placebo group.

The safety analyses will use the Safety Population defined in **Section 8.3**.

The frequency of SAEs, AEs leading to withdrawal from study participation, and TEAEs will be included in the primary safety tables.

Adverse events will be coded using the Medical Dictionary for Regulatory Activities (MedDRA) classifications with reference to system organ classes (SOCs) and preferred terms. Only TEAEs will be included in summary tables. Summaries of TEAEs will be presented by SOC and preferred term, by treatment. Summaries will include the frequency of TEAEs, SAEs, and AEs leading to withdrawal from study participation, by dose as well as by intensity and relationship to study drug.

Out of range laboratory tests, ECGs, and vital signs of potential clinical importance will also be summarized; a listing of patients with at least one out of range value will be presented by visit for that test.

Laboratory tests (hematology, serum chemistry, and urinalysis), vital signs, and ECG will be summarized as changes from baseline. Laboratory shift tables will also be produced, where applicable. Listings of laboratory tests, vital signs, and ECGs will also be provided.

Physical examination and medical history listings will be provided but not summarized.

Concomitant medications will be auto-encoded using the WHODD coding system with reference to Anatomical Therapeutic Classification (ATC) text and preferred terms. Summaries of concomitant medication will be presented by ATC text and preferred terms. Prior, concomitant, prior and concomitant, and post-treatment medications will be presented separately.

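### Five diary symptoms are generally kept out of AE recording because the diary is a safety record, but no safety endpoint or safety analysis uses the diary

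*Combined protocol and SAP*

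**What the plan says.** Section 4.3.1 names five symptoms rated daily in the diary (abdominal bloating, abdominal pain, abdominal discomfort, straining, pain with defecation) and says that "these events should generally NOT be recorded elsewhere as adverse events". Section 7.1 repeats the rule. It says these symptoms "are BOTH efficacy AND safety response variables", and that the diary record "should therefore be the only record of the same event". Its reasons are the diary's 24-hour recall and the wish to avoid recording one event twice. Section 7.4 states without exception that all AEs of randomized patients go in the eCRF.

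The safety endpoints in 2.4.3 are TEAEs and withdrawals due to AEs and SAEs, followed by the statement "Clinically important changes in laboratory tests, vital signs, and ECGs will be presented". In 8.10 the safety evaluation "will be based on the occurrence of TEAEs, vital signs, clinical laboratory assessments, and ECGs", and "Summaries will include the frequency of TEAEs, SAEs, and AEs leading to withdrawal from study participation". Neither section names the diary.

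The five symptoms are analyzed in 8.8.3.1 as additional efficacy endpoints: "The change from baseline in mean weekly average symptom score will be analyzed using a linear mixed-effects model", with a weekly summary by arm. Section 8.4 sets the content of such summaries: n, mean, SD, median, minimum and maximum, for observed values and for change from baseline. Section 8.3 bases efficacy analyses on the ITT Population and safety analyses on the Safety Population. PAC-SYM also covers the five symptoms (items 1, 2, 3, 5 and 11) with a two-week recall. For the questionnaires, 8.8.5 says "Summary analyses of these data will also be provided as described in the SAP".

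**The concern.** The ground for leaving these events out of the AE database is that the diary does the safety work. No safety section then uses the diary, so the premise is not carried through.

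Safety is part of the primary objective (2.2.1), and the protocol expects gastrointestinal effects. Abdominal pain and abdominal distension were among the TEAEs seen in at least 2% of patients in the adult dose-ranging study (2.1.4), and 2.3 names bloating. If sites follow the instruction, the TEAE comparison with placebo will be incomplete for these terms. Part of the loss is permanent: a diary entry holds a 0 to 10 rating, whereas an AE report under 7.4 also holds treatment required, relationship to study drug, action taken and outcome.

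**Working it through.** The plan states no figure on this point, so there is none to reproduce. The check follows one event through the plan and then asks what the planned and proposed outputs would show.

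**1. Where a non-serious worsening of abdominal pain would appear**

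| Output | Source | Shows it? |
|---|---|---|
| TEAE tables | 8.10, fed by 4.3.1 and 7.1 | Generally not |
| Relationship, treatment, action taken, outcome | 7.4 | Generally not recorded |
| Weekly n, mean, SD, median, minimum, maximum of change | 8.4, 8.8.3.1 | Yes, as an efficacy summary in the ITT Population |
| LS mean differences by week | 8.8.3.1 | Only through the mean |
| PAC-SYM | 8.8.5 | At visits, with the form of the summary left to the SAP |
| Number or percentage of patients who worsen | none | Not planned |
| Each patient's worst or sustained change | none | Not planned |
| Any Safety Population summary of the diary | none | Not planned |

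**2. What the planned weekly table shows.** Take an arm of 30 (Section 2.6) with assumed changes of +5 in 3 patients and -1 in 27.
- Mean = (3 × 5 − 27 × 1)/30 = −12/30 = −0.4
- SD = √[(3 × 5.4² + 27 × 0.6²)/29] = √(97.2/29) = 1.83
- Maximum = +5

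The mean reads as improvement, but the maximum shows that somebody worsened by 5 points. It does not say whether that was one patient or three, or whether the same patient supplies the maximum in successive weeks.

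**3. Means, maxima and counts compared.** All inputs here are assumptions: normal weekly changes, both arms averaging −1, SD 1.5 to 2.5, between-week correlation 0.5 to 0.8, and 3 of 30 active patients shifted by +6 in every week. A t-test stands in for the planned weekly contrast.
- The expected arm difference is 3 × 6/30 = 0.6, against a 95% half-width of 1.02 to 1.45. It reaches p<0.05 in about 10% to 15% of trials.
- The active arm's weekly maximum exceeds the placebo maximum in about 93% to 100% of trials.
- Patients at +3 or more in two consecutive weeks average 3.0 to 4.4 of 30 on active and 0.1 to 1.9 on placebo. Fisher's exact test on these counts reaches p<0.05 in about 0% to 3% of trials; 3/30 against 0/30 gives p = 0.24.

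The counts are therefore no more powerful than the mean contrast. They are useful because they say how many patients worsened and for how long.

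**4. Precision and background rate of the counts.** The half-width for a difference between arms is 1.96 × √[2p(1−p)/30]: 15.2 percentage points at p = 0.10, 21.2 at 0.228, 25.3 at 0.50 and 24.8 at 0.595. With no drug effect, mean change 0 and the same SDs and correlations, 23% to 60% of patients reach +2 in at least one of 8 weeks, and 10% to 27% do so in two consecutive weeks. A count without placebo beside it would mislead.

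**The case against.** The strongest reply is that the diary data are already compared by arm, and in some detail. A reader might infer from the mean of −0.4 that the planned outputs would hide a worsening minority. The documents do not support that: 8.4 requires the minimum and maximum of change at each time point, and the example would print a maximum of +5. This part of the reply stands. The gap is a count, a per-patient view over time, a Safety Population summary and the AE attributes.

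Section 8 also leaves details of the safety and efficacy methods to an SAP written before unblinding. That SAP could add the table. It could not recover relationship, treatment or action-taken data that sites were generally told not to enter.

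Third, 7.1 may be read as a reasoned exception to the general rule in 7.4, and the word generally leaves investigators discretion. SAEs are reported in every case (7.5). That limits the point to non-serious events. Discretion without a criterion invites uneven recording across sites, however, and 7.2 shows that an explicit criterion can be written, as it is for diarrhea.

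Fourth, a reader might infer that withdrawals for these symptoms will be missing from the table of AEs leading to withdrawal. That is possible but not established: 5.2.6 counts clinically significant TEAEs among the events that qualify for early withdrawal, so an investigator may well enter them.

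Finally, the adult Phase 3 lists of TEAEs at 2% or more (2.1.4) name none of the five symptoms. That tempers the expected frequency, but the documents do not say whether the same recording rule applied in those studies.

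**Conclusion.** The point holds in a limited form and is worth acting on. The plan relies on the diary as the safety record for five expected symptoms, yet gives the diary no place in the safety endpoints or analyses. If the instruction is followed, the TEAE comparison will be incomplete for non-serious worsening of these symptoms, and the AE attributes will generally be lost. Large individual changes would still be visible in the weekly efficacy summaries, so this is not a finding that harm would go unseen.

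The textual conclusion rests on no numerical assumption. The simulated figures depend on the assumed SDs, correlations and a persistent 6-point shift, with no bound at the ends of the 0 to 10 scale; they serve only to show what counts add and what they do not. How often such worsening will occur cannot be derived from the documents.

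**What to change.** (1) Add to 8.10 a descriptive summary on the Safety Population, by arm including placebo. For each of the five symptoms, give the number and percentage of patients whose weekly average worsens from baseline by at least X points in any treatment week, and in two consecutive treatment weeks. Add the distribution of each patient's worst change and the number of patients without evaluable scores. Fix and justify X before unblinding; 2 and 3 points are used above only as assumptions.

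(2) Reconcile 4.3.1, 7.1 and 7.4 into one rule for when a diary symptom is also entered as an AE. The rule should cover the case where the symptom is the reason for withdrawal, so that the 8.10 table of AEs leading to withdrawal can agree with the discontinuation reasons summarized under 8.5.

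The cost is one table set from data already collected and one recording rule stated consistently in three sections, with no added patients, visits or assessments. Some events will be displayed both in the diary table and as AEs, which a footnote can explain. The counts have low precision, support description only, and should not be presented as a more sensitive test than the planned mean contrast.
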